20.3. POPULATION PK ANALYSIS

The strategy for the population PK analysis and any related exposure-response modeling utilizing the ensifentrine concentration and response data from this study will be outlined separately in the modeling data analysis plan prepared by Verona Pharma/Designee.

21. DATA NOT SUMMARIZED OR PRESENTED

The other variables and/or domains not summarized or presented are:

- Comments
- Physical Examinations, as it is not collected within eCRF

These domains and/or variables will not be summarized or presented, but if collected will be available in the clinical study database, SDTM and/or ADaM datasets.

L

FINAL v1.0
25JUL2022

APPENDIX 1. PROGRAMMING CONVENTIONS FOR OUTPUTS

DATES & TIMES

Depending on data available, dates and times will take the form yyyy-mm-ddThh:mm:ss.

SPELLING FORMAT

English US.

PRESENTATION OF TREATMENT GROUPS

For outputs, treatment groups will be represented as follows and in the given order:

Treatment Group	For Tables, Listings and Graphs
Ensifentrine	Ensifentrine
Placebo	Placebo
Not Randomized	Not Randomized

DECIMAL PLACES

The decimal places for this study will use the following rules, unless otherwise stated.

Value = x dp

Mean = x+1 dp

Standard Deviation = x+2 dp

Median = x+1 dp

Q1/Q3 = x+1 dp

Minimum/Maximum = x dp

CI = x+1 dp

In case a variable has values with infinite decimal places, the following rules will be used:

Value = 1 dp

Mean = 2 dp

Standard Deviation = 3 dp

Median = 2 dp

Q1/Q3 = 2 dp

Minimum/Maximum = 1 dp

CI = 2 dp

For spirometry data we will present outputs with decimal places for value as follows:

- Values in liters = 3 dp, i.e. mean/median/Q1/Q3/CI in liters = 4 dp, standard deviation = 5 dp and minimum/maximum = 3 dp.
- Values in milliliters = 0 dp, i.e. mean/median/Q1/Q3/CI in liters = 1 dp, standard deviation = 2 dp and minimum/maximum = 0 dp.
- Percentage values = 1 dp, i.e. mean/median/Q1/Q3/CI in liters = 2 dp, standard deviation = 3 dp and minimum/maximum = 1 dp.

P-values will be presented to 4dp.

PRESENTATION OF VISITS

For outputs, visits will be represented as follows and in that order:

Long Name (default)	Short Name
Screening	Screening
day 1	day 1
week 6	week 6
week 12	week 12
week 18	week 18
week 24	week 24
Follow-up	Follow-up

LISTINGS

All listings will be ordered by the following (unless otherwise indicated in the template):

- Randomized treatment group (or treatment received if it's a safety output), first by active dose and then placebo,
- Center-patient ID,
- Date and time (where applicable),
- For listings where non-randomized patients are included, these will appear in a category

after the randomized treatment groups labeled 'Not Randomized'.

TABLES

All tables presenting multiple events that map to a SOC and PT will be counted only once, per unique patient, for incidence counts. Events will be presented in descending frequency of SOC and PT (unless otherwise indicated in the shells).

APPENDIX 2. PARTIAL DATE CONVENTIONS

Imputed dates will NOT be presented in the listings.

ALGORITHM FOR TREATMENT EMERGENCE OF ADVERSE EVENTS:

START DATE	STOP DATE	ACTION
Known	Known/Partial/ Missing	If start date < study med start date, then not TEAE If start date >= study med start date, then TEAE
Partial, but known components show that it cannot be on or after study med start date	Known/Partial/ Missing	Not TEAE
Partial, could be on or after study med start date OR Missing	Known	If stop date < study med start date, then not TEAE If stop date >= study med start date, then TEAE
	Partial	Impute stop date as latest possible date (i.e. last day of month if day unknown or 31st December if day and month are unknown), then: If stop date < study med start date, then not TEAE If stop date >= study med start date, then TEAE
	Missing	Assumed TEAE

**ALGORITHM FOR PRIOR/ PRIOR CONCOMITANT / CONCOMITANT
 MEDICATIONS:**

[figure not shown]
START DATE	STOP DATE	ACTION
Known	Known	If stop date < study med start date, assign as prior If stop date >= study med start date and start date < study med start, assign as prior concomitant If stop date >= study med start date and (start date > study med start or start date <= end of treatment), assign as concomitant If start date > end of treatment, assign as post study
	Partial	Impute stop date as latest possible date (i.e. last day of month if day unknown or 31st December if day and month are unknown), then: If stop date < study med start date, assign as prior If stop date >= study med start date and start date < study med start, assign as prior concomitant If stop date >= study med start date and (start date > study med start or start date <= end of treatment), assign as concomitant If start date > end of treatment, assign as post study
	Missing	If stop date is missing could never be assumed a prior medication If stop date >= study med start date and start date < study med start, assign as prior concomitant If stop date >= study med start date and (start date > study med start or start date <= end of treatment), assign as concomitant If start date > end of treatment, assign as post study

START DATE	STOP DATE	ACTION
Partial	Known	
Impute start date as earliest possible date (i.e. first day of month if day unknown or 1st January if day and month are unknown), then:
 
If stop date < study med start date, assign as prior
 
If stop date >= study med start date and start date < study med start, assign as prior concomitant
 
If stop date >= study med start date and (start date > study med start or start date <= end of treatment), assign as concomitant
 
If start date > end of treatment, assign as post study

	Partial	
Impute start date as earliest possible date (i.e. first day of month if day unknown or 1st January if day and month are unknown) and impute stop date as latest possible date (i.e. last day of month if day unknown or 31st December if day and month are unknown), then:
 
If stop date < study med start date, assign as prior
 
If stop date >= study med start date and start date < study med start, assign as prior concomitant
 
If stop date >= study med start date and (start date > study med start or start date <= end of treatment), assign as concomitant
 
If start date > end of treatment, assign as post study

	Missing	
Impute start date as earliest possible date (i.e. first day of month if day unknown or 1st January if day and month are unknown), then:
 
If stop date is missing could never be assumed a prior medication
 
If stop date >= study med start date and start date < study med start, assign as prior concomitant
 
If stop date >= study med start date and (start date > study med start or start date <= end of treatment), assign as concomitant
 
If start date > end of treatment, assign as post study

START DATE	STOP DATE	ACTION
Missing	Known	If stop date < study med start date, assign as prior If stop date >= study med start date, assign as concomitant Cannot be assigned as 'prior concomitant' and 'post treatment'
	Partial	Impute stop date as latest possible date (i.e. last day of month if day unknown or 31st December if day and month are unknown), then: If stop date < study med start date, assign as prior If stop date >= study med start date, assign as concomitant Cannot be assigned as 'prior concomitant' and 'post treatment'
	Missing	Assign as concomitant

ALGORITHM FOR CONCOMITANT ILLNESSES:

START DATE	STOP DATE	ACTION
Known	Known	If stop date > date of first treatment dose and start date <= date of first treatment dose, assign as concomitant illness
	Partial	Impute stop date as latest possible date (i.e. last day of month if day unknown or 31st December if day and month are unknown), then: If stop date > date of first treatment dose and start date <= date of first treatment dose, assign as concomitant illness
	Missing	If stop date is missing then assume concomitant illness
Partial	Known	Impute start date as earliest possible date (i.e. first day of month if day unknown or 1st January if day and month are unknown), then: If stop date > date of first treatment dose and start date <= date of first treatment dose, assign as concomitant illness
	Partial	Impute start date as earliest possible date (i.e. first day of month if day unknown or 1st January if day and month are unknown) and impute stop date as latest possible date (i.e. last day of month if day unknown or 31st December if day and month are unknown), then: If stop date > date of first treatment dose and start date <= date of first treatment dose, assign as concomitant illness
	Missing	Impute start date as earliest possible date (i.e. first day of month if day unknown or 1st January if day and month are unknown), then: If stop date is missing then assume concomitant illness
Missing	Known	If stop date > date of first treatment dose, assign as concomitant illness

START DATE	STOP DATE	ACTION
	Partial	Impute stop date as latest possible date (i.e. last day of month if day unknown or 31st December if day and month are unknown), then: If stop date > date of first treatment dose, assign as concomitant illness
	Missing	If stop date is missing then assume concomitant illness

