17.1. ADVERSE EVENTS

Adverse Events (AEs) will be coded using MedDRA central coding dictionary. The version of MedDRA to be used will be specified prior to database lock.

Treatment-emergent adverse events (TEAEs) are defined as AEs that started or worsened in severity on or after the first dose of study medication. Laboratory or ECG findings from procedures or samples drawn prior to the first doses of study medication that are assessed/overread after randomization will be considered pre-treatment.

In the case where it is not possible to define an AE as treatment-emergent or not, the AE will be classified by the worst case; i.e. treatment-emergent.

See Appendix 2 for handling of partial dates for AEs.

An overall summary of number of patients within each of the categories described in the subsection below, will be provided as specified in the shells. In addition, the number of patients with each of the following AE events will be presented by SOC and PT and summarized by treatment group and different period (i.e. Treatment period, Follow-up and Overall):

- TEAE
- TEAEs causally related to study medication

- Serious TEAEs
- TEAEs with an outcome of death
- TEAEs leading to discontinuation of blinded study medication
- TEAEs leading to withdrawal from study (TEAEs with a diagnosis of COVID-19, TEAEs with no diagnosis of COVID-19)
- TEAEs by maximum severity

AEs will be identified by using the “Adverse Events” page of the eCRF. Listings will include TEAEs and Non-TEAEs.

Treatment period is defined as the period from the date and time of first dose up to the date and time of last dose.

Follow-up is defined as the period from after the date and time of last dose up to the last date recorded on the study.

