17.1.3. SERIOUS ADVERSE EVENTS

Serious adverse events (SAEs) are those events recorded as "Serious" on the "Adverse Events" page of the eCRF. A summary of serious TEAEs by SOC and PT and by treatment group and different period (i.e. Treatment period, Follow-up and Overall) will be prepared.

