17.1.4. ADVERSE EVENTS LEADING TO DEATH

TEAEs leading to Death are those events which are recorded as "Fatal" on the "Adverse Events" page of the eCRF. A summary of TEAEs leading to death by SOC and PT will be prepared.

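### SAP Appendix 2 decides treatment emergence by dates alone and contradicts SAP 17.1 in at least two cases: a pre-dose AE that worsens after dosing, and a lab/ECG finding from a Day 1 pre-dose assessment

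*SAP*

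**What the plan says.** SAP 17.1 defines TEAEs as "AEs that started or worsened in severity on or after the first dose of study medication". It has a separate rule for laboratory and ECG results: "findings from procedures or samples drawn prior to the first doses of study medication that are assessed/overread after randomization will be considered pre-treatment". It also sets a default, "In the case where it is not possible to define an AE as treatment-emergent or not", under which the event is counted as treatment-emergent. It then refers to Appendix 2 for partial dates.

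SAP 6.2 agrees with the laboratory/ECG sentence: abnormalities from pre-dose assessments stay baseline even when they are read after dosing. It also treats an AE that begins on the first-dose date as post-baseline.

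Appendix 2 contains a table presented as the algorithm for treatment emergence. Row 1 covers fully known start dates: "If start date < study med start date, then not TEAE", and TEAE if the start is on or after the first-dose date. Row 2, "Partial, but known components show that it cannot be on or after study med start date", returns not TEAE whatever the stop date. No row mentions severity or the laboratory/ECG rule.

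On outputs, SAP 17.1 says "Listings will include TEAEs and Non-TEAEs". The serious-event and fatal-event tables are planned for TEAEs only: "A summary of serious TEAEs by SOC and PT and by treatment group" (17.1.3) and "A summary of TEAEs leading to death by SOC and PT will be prepared" (17.1.4).

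**The concern.** The SAP gives two instructions for the same record and does not say which one prevails. A programmer would naturally code the table, because it looks like a complete classifier.

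In case (a), an event that is a TEAE by the SAP's own definition would be missing from every TEAE table and seen only in the listings. The records most likely to qualify are serious, so the serious and fatal TEAE tables are among those concerned. In case (b), an abnormality already present before dosing would be tabulated as treatment-emergent. Because the errors run in opposite directions, repairing one does not repair the other.

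**Working it through.** No figure in the plan bears on this point, so the check is of rule logic.

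**Step 1: enumerate.** Take AE records with a complete start date and cross three features:
- start: before Day 1; Day 1 before the dose by clock time; Day 1 after the dose; after Day 1 (4 levels);
- severity increased on or after first dose: no or yes (2 levels);
- finding from a pre-dose laboratory sample or ECG read later: no or yes (2 levels).

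This gives 4 × 2 × 2 = 16 combinations. Appendix 2 is applied as *TEAE if start date ≥ first-dose date*. SAP 17.1 is applied as *TEAE if started or worsened after the dose, except that a pre-dose lab/ECG finding that did not worsen is pre-treatment*. They disagree in six:

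| Start | Worsened | Pre-dose lab/ECG | Appendix 2 | SAP 17.1 | Case |
|---|---|---|---|---|---|
| Before Day 1 | yes | no | not TEAE | TEAE | (a) |
| Before Day 1 | yes | yes | not TEAE | TEAE | (a) |
| Day 1, before dose | no | no | TEAE | not TEAE | settled by 6.2 |
| Day 1, before dose | no | yes | TEAE | not TEAE | (b) |
| Day 1, after dose | no | yes | TEAE | not TEAE | (b) |
| After Day 1 | no | yes | TEAE | not TEAE | (b) |

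The third line is set aside because SAP 6.2 treats an AE beginning on the first-dose date as post-baseline. That leaves 6 − 1 = 5 combinations: 2 for case (a) and 3 for case (b). These counts depend on how the grid is drawn and do not measure frequency. Row 2 behaves like a start before Day 1.

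**Step 2: which records can reach case (a).**
- Protocol 8.7.1 collects AEs from first dose, except SAEs related to study participation, which are collected from consent. The pre-dose period is the run-in, 28 − 4 = 24 to 28 + 4 = 32 days, plus any time between consent and Screening.
- Protocol 5.3 bars randomization after a COPD exacerbation or lower respiratory tract infection in that period.
- Conditions ongoing at first dose are held as concomitant illnesses from the Medical History page (SAP 12). Protocol 11.7 makes a flare of such a condition an AE in its own right. Entered with the date of the flare, it is classified correctly by row 1.
- What mainly remains is a participation-related SAE still ongoing at first dose that then becomes more severe. Protocol 11.7 sends follow-up information to the existing record, but it also wants each event recorded separately and counts increased intensity of a pre-existing condition as an AE. The documents do not settle which start date such a worsening would carry.

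**Step 3: which records can reach case (b).**
- Day 1 is the first-dose date (SAP 6.1). Triplicate ECGs are taken before the dose that day (Protocol 8.4.2.1) and over-read centrally (8.4.2). Laboratory tests are scheduled at Visit 1 (Protocol 1.3) and drawn before dosing (11.3).
- Protocol 11.7 accepts as AEs both clinically significant laboratory/ECG abnormalities and conditions first detected after dosing that may have existed earlier.
- Such an AE, dated Day 1 or the day of reading, meets row 1's second line and becomes a TEAE. SAP 17.1 calls the same finding pre-treatment.

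**The case against.** The strongest reply concerns hierarchy. Appendix 2 is titled as a set of partial-date conventions, and 17.1 cites it only for that purpose. On this reading 17.1 governs and the table is a subordinate aid. That may well be the intention. But row 1 is the known-date row, the table is labelled as the treatment-emergence algorithm, and no precedence is stated, so the conflict remains on the page.

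A second reply is that the worst-case default in 17.1 protects against omission. It does not, because it operates only when classification is impossible, and rows 1-2 give a definite answer.

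A third reply is that worsening would always be entered as a new AE with its own date. This cannot be ruled out. If it is the practice, case (a) is empty, but the SAP should say so. The reply does not touch case (b).

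A fourth reply is that the practical effect is close to nil. For case (a) this largely stands: the event must be serious, participation-related, ongoing at first dose, worse afterwards and not re-recorded.

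Two stronger readings are tempting. A reader might infer that worsening is the only disagreement, so that one added clause aligns the texts; case (b) shows otherwise. A reader might also infer that a worsened SAE necessarily keeps its pre-dose start date. The follow-up instruction in Protocol 11.7 does not go that far, and its other provisions leave the question open.

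**Conclusion.** Appendix 2 is wrong as written, and the point is minor. Rows 1-2 omit the worsening limb of the definition, and row 1 omits the laboratory/ECG rule, so the algorithm departs from SAP 17.1 in at least two cases.

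The number of records cannot be estimated from the documents. Case (a) is expected to affect few and possibly none, and it depends on worsening not being entered as a separate AE. Case (b) depends on a pre-dose finding being entered as an AE with a start date of Day 1 or later. The enumeration assumes that a pre-dose finding that later worsens counts as a TEAE under 17.1. If the laboratory/ECG sentence were read to override worsening, the affected combinations would change but both cases would remain.

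The documents do not support a claim that the safety tables are materially understated or that the arms would be affected differently. Case (a) lowers the TEAE count and case (b) raises it, no difference between arms is expected, the records stay in the listings, and efficacy is untouched.

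**What to change.** Change the SAP only:

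1. Appendix 2, rows 1-2, after the not-TEAE result, add: *unless its severity increased on or after first dose, in which case TEAE*.
2. Appendix 2, row 1, after the TEAE result, add: *except lab/ECG findings from pre-dose samples or procedures, which are not TEAE (Section 17.1)*.
3. State that Section 17.1 prevails wherever it and Appendix 2 differ. This also covers laboratory/ECG findings with partial or missing start dates.
4. Before database lock, review blinded all AE records with a pre-dose start date and all laboratory/ECG AEs traced to Day 1 pre-dose assessments. The review is needed to apply item 1, because Protocol 11.7 describes one intensity category per AE and no dated change in severity.

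No protocol recording instruction needs to change. The cost is two clauses, one sentence and a little more review work. The TEAE count may move slightly in either direction.

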APPENDIX 3. ANNOTATED EXACT FOR RAW SCORE ASSIGNMENT

1. Did your chest feel congested today?	0. Not at all
	1. Slightly
	2. Moderately
	3. Severely
	4. Extremely
2. How often did you cough today?	0. Not at all
	1. Rarely
	2. Occasionally
	3. Frequently
	4. Almost constantly
3. How much mucus (phlegm) did you bring up when coughing today?	0. None at all
	1. A little
	1. Some
	2. A great deal
	3. A very great deal
4. How difficult was it to bring up mucus (phlegm) today?	0. Not at all
	1. Slightly
	2. Moderately
	3. Quite a bit
	4. Extremely
5. Did you have chest discomfort today?	0. Not at all
	1. Slight
	2. Moderate
	3. Severe
	4. Extreme
6. Did your chest feel tight today?	0. Not at all
	1. Slightly
	2. Moderately
	3. Severely
	4. Extremely
7. Were you breathless today?	0. Not at all
	1. Slightly
	2. Moderately
	3. Severely
	4. Extremely

8. Describe how breathless you were today	0. Unaware of breathlessness
	1. Breathless during strenuous activity
	2. Breathless during light activity
	3. Breathless when washing or dressing
	3. Present when resting
9. Were you short of breath today when performing your usual personal care activities like washing or dressing?	0. Not at all
	1. Slightly
	2. Moderately
	3. Severely
	3. Extremely
10. Were you short of breath today when performing your usual indoor activities like cleaning or household work?	0. Not at all
	1. Slightly
	2. Moderately
	3. Severely
	3. Extremely
11. Were you short of breath today when performing your usual activities outside the home such as yard work or errands?	0. Not at all
	1. Slightly
	2. Moderately
	3. Severely
	3. Extremely
12. Were you tired or weak today?	0. Not at all
	1. Slightly
	2. Moderately
	3. Severely
	4. Extremely
13. Last night, was your sleep disturbed?	0. Not at all
	1. Slightly
	2. Moderately
	3. Severely
	4. Extremely
14. How scared or worried were you about your lung problems today?	0. Not at all
	1. Slightly
	2. Moderately
	3. Severely

	3.Extremely
--	-------------

**APPENDIX 4. RAW SUMMED SCORE TO SCALE CONVERSION
 TABLE FOR EXACT TOTAL SCORE**

Raw Summed Score	EXACT Total Score	Raw Summed Score	EXACT Total Score
0	0	26	50
1	8	27	51
2	13	28	52
3	17	29	53
4	20	30	54
5	23	31	55
6	25	32	57
7	27	33	58
8	28	34	59
9	30	35	60
10	31	36	61
11	33	37	63
12	34	38	64
13	36	39	65
14	37	40	67
15	38	41	68
16	39	42	70
17	40	43	72
18	41	44	73
19	42	45	75
20	43	46	77
21	44	47	80
22	46	48	83
23	47	49	87
24	48	50	92
25	49	51	100

APPENDIX 5. SGRQ ITEM WEIGHTS

Question	Answers	Weight
Part 1		
Question 1: Over the past 4 weeks, I have coughed	Almost every day	80.6
	Several days a week	63.2
	A few days a month	29.3
	Only with respiratory infections	28.1
	Not at all	0.0
Question 2: Over the past 4 weeks, I have brought up phlegm (sputum)	Almost every day	76.8
	Several days a week	60.0
	A few days a month	34.0
	Only with respiratory infections	30.2
	Not at all	0.0
Question 3: Over the past 4 weeks, I have shortness of breath	Almost every day	87.2
	Several days a week	71.4
	A few days a month	43.7
	Only with respiratory infections	35.7
	Not at all	0.0
Question 4: Over the past 4 weeks, I have wheezing attacks	Almost every day	86.2
	Several days a week	71.0
	A few days a month	45.6
	Only with respiratory infections	36.4
	Not at all	0.0
Question 5: How many times during the past 4 weeks have you suffered from severe or very unpleasant respiratory attacks?	More than 3 times	86.7
	3 times	73.5
	2 times	60.3
	1 time	44.2
	None of the time	0.0
Question 6: How long did the worst respiratory attack last?	A week or more	89.7
	3 or more days	73.5

(Go to Question 7 if you did not have a severe attack)	1 or 2 days	58.8
	Less than a day	41.9
Question 7: Over the past 4 weeks, in a typical week, how many good days (with few respiratory problems) have you had?	No good days	93.3
	1 or 2 good days	76.6
	3 or 4 good days	61.5
	Nearly every day was good	15.4
	Every day was good	0.0
Question 8: If you wheeze, is it worse when you get up in the morning?	No	0.0
	Yes	62.0
Part 2		
Question 9: How would you describe your respiratory condition?	The most important problem I have	83.2
	Causes me quite a lot of problems	82.5
	Causes me a few problems	34.6
	Causes no problem	0.0
Question 10: If you ever held a job	My respiratory problems made me stop working altogether	88.9
	My respiratory problems interfere with my job or made me change my job	77.6
	My respiratory problems do not affect my job	0.0
Question 11: Questions about what activities usually make you short of breath these days	Sitting or lying still	90.6
	Washing or dressing yourself	82.8
	Walking around the house	80.2
	Walking outside on level ground	81.4
	Walking up a flight of stairs	76.1
	Walking up hills	75.1
	Playing sports or other physical activities	72.1
Question 12: More questions about your cough and shortness of breath these days	Coughing hurts	81.1
	Coughing makes me tired	79.1

	I am short of breath when I talk	84.5
	I am short of breath when I bend over	76.8
	My coughing or breathing disturbs my sleep	87.9
	I get exhausted easily	84.0
Question 13: Questions about other effects your respiratory problems may have on you these days		
	My cough or breathing is embarrassing in public	74.1
	My respiratory problems are a nuisance to my family, friends or neighbors	79.1
	I get afraid or panic when I cannot catch my breath	87.7
	I feel that I am not in control of my respiratory problems	90.1
	I do not expect my respiratory problems to get any better	82.3
	I have become frail or an invalid because of my respiratory problems	89.9
	Exercise is not safe for me	75.7
	Everything seems too much of an effort	84.5
Question 14: Questions about your respiratory treatment		
	My treatment does not help me very much	88.2
	I get embarrassed using my medication in public	53.9
	I have unpleasant side effects from my medication	81.1
	My treatment interferes with my life a lot	70.3
Question 15: Questions about how activities may be affected by your respiratory problems		
	I take a long time to get washed or dressed	74.2
	I cannot take a bath or shower, or I take a long time	81.0

	I walk more slowly than other people, or I stop to rest	71.7
	Jobs such as housework take a long time, or I have to stop to rest	70.6
	If I walk up one flight of stairs, I have to go slowly or stop	71.6
	If I hurry or walk fast, I have to stop or slow down	72.3
	My breathing makes it difficult to do things such as walk up hills, carry things up stairs, light gardening such as weeding, dance, play bowls or play golf	74.5
	My breathing makes it difficult to do things such as carry heavy loads, dig in the garden or shovel snow, jog or walk briskly (5 miles per hour), play tennis or swim	71.4
	My breathing makes it difficult to do things such as very heavy manual work, ride a bike, run, swim fast, or play competitive sports	63.5
Question 16: We would like to know how your respiratory problems usually affect your daily life		
	I cannot play sports or other physical activities	64.8
	I cannot go out for entertainment or recreation	79.8
	I cannot go out of the house to do the shopping	81.0
	I cannot do household chores	79.1
	I cannot move far from my bed or chair	94.0
Question 17: Tick the statement which you think best describes how your respiratory problems affect you		
	It does not stop me from doing anything I would like to do	0.0

	It stops me from doing one or two things I would like to do	42.0
	It stops me from doing most of the things I would like to do	84.2
	It stops me from doing everything I would like to do	96.7

